2.15.2 Analysis of secondary outcomes: growth measures and blood pressure

These secondary outcomes are continuous and will be compared between treatment arms using two-sample t-tests. Multiple linear (least-squares) regression will be used to adjust for the baseline variables. Transformation or ranking procedures will be used if the data are observed to be skewed. A nominal Type I error of 0.0125 will be used to maintain an overall Type I error of 0.05. Since pregnancy is the unit of analysis, the worst value for the children of multiple births will be used.

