4ii) *Child Behavior Checklist (CBCL)-Parent Form*: The Parent Form for ages 1½-5 years is used as an additional measure of both attention and behavioural skills.^{47,48} This is one of the most commonly used tools to measure behaviours in children and has been used in studies evaluating behaviours in preterm children. The psychometric properties include high test-retest reliability (0.95-1.0), inter-rater reliability (0.93-0.96), and internal consistency (0.78-0.97) and validity estimates from .55 to .75. The CBCL has undergone numerous studies to assess content and construct validity. Comparisons with clinical status (referred/non-referred) also support the validity of the instrument.^{47,48} The Total Behaviors Problems T scores contributes to the primary outcome. An abnormal outcome is defined as a score that is 1.5 SD above the mean of the normative control sample; again, a higher score reflects abnormality.

The CBCL and BRIEF-P will be made available in all of the languages that are required for the study.

2.8.2 Secondary outcomes for MACS-5:

Secondary outcomes to be assessed in all children include *measures of growth and blood pressure*:

- 1i) height (cm)
- 1ii) weight (kg)
- 1iii) head circumference (cm)
- 1iv) systolic and diastolic blood pressure (mmHg)

Secondary outcomes to be assessed in children in English speaking centres include *intelligence and specific cognitive skills (visual motor, visual spatial, and language skills)*: For logistical reasons, only English-speaking centers that have trained psychologists or psychometrists that are available to administer these more specific psychological tests will participate in these assessments:

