2.11.2 Sample size for secondary outcomes: growth measures and blood pressure

Four power curves for the secondary outcomes of growth measures and blood pressure, assuming 55%, 60%, 65% or 70% follow-up, are given in Figure 2.11.2. A 2-sided type I error of 5% is used. (A nominal value of $0.05/4 = 0.0125$ was used to control type I error because there are 4 outcomes in this category.) The range of differences for which we have an 80% power is 0.18 to 0.21 standard deviations.

[figure not shown]
Figure 2.11.2 Power Curves for Growth Measures and Blood Pressure

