2.11.3 Sample size for secondary outcomes: intelligence and specific cognitive skills

We estimate that over 300 women will be recruited in English-speaking centres and that approximately 250 of the children will be followed until 5 years of age. Thus the children of 250 women from participating English-speaking centers will be available to evaluate these outcomes. The power curve for this sample size is given in Figure 2.11.3. The difference for which we have an 80% power is 0.42 standard deviations. For the WPPSI, this corresponds roughly to absolute differences of 5-7 points on the scale.³² (A nominal value of $0.05/3 = 0.0167$ was used to control type I error because there are 3 outcomes in this category.)

Figure 2.11.3 Power Curves for Intelligence and Specific Cognitive Skills

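### An improvement, not an error: Holm's step-down would raise power in both secondary families at the same overall 0.05, once the family sizes are settled

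*Protocol*

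**What the plan says.** Protocol section 2.15.2 (growth and blood pressure) compares the arms by two-sample t-tests and sets one level for every outcome: "A nominal Type I error of 0.0125 will be used to maintain an overall Type I error of 0.05". Section 2.15.3 (intelligence and cognitive skills) repeats that sentence word for word. Neither section mentions a step-down procedure.

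The sample size sections give the reasoning behind the level. Section 2.11.2 takes 0.05/4 = 0.0125 for growth and blood pressure, which "was used to control type I error because there are 4 outcomes in this category". Section 2.11.3 takes 0.05/3 = 0.0167 for the cognitive outcomes, which "was used to control type I error because there are 3 outcomes in this category". The analysis section for the cognitive family does not carry the 0.0167 over.

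Section 2.8.2 lists height, weight, head circumference and, as a single item, "systolic and diastolic blood pressure (mmHg"). The count of four therefore holds only if the two pressures form one test.

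**The concern.** Under a single-step rule each outcome faces the same threshold whatever the others show. Holm compares the smallest p-value with 0.05/k, the next with 0.05/(k-1), and so on, and stops at the first failure. It gives the same strong control of the overall error without assuming independence. For a given family size, it can only add rejections to those of Bonferroni at 0.05/k.

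These are largely safety outcomes. The background sections report lower birth weight with repeat courses and growth delay in animals, so a joint shift in several growth measures is plausible. The cognitive family rests on about 250 women. If several outcomes in a family are truly affected, the fixed rule declares fewer of them than the same overall error rate would allow.

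**Working it through.** **Inputs.** Section 2.11.1: N = 1045 to 1330 pregnancies. Section 2.11.3: 250 women. Sections 2.11.2 and 2.11.3: detectable differences of 0.18 to 0.21 SD and 0.42 SD at 80% power. Assumed, because the protocol does not state them: 1:1 allocation, and a common correlation between outcomes of 0 to 0.7.

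**Step 1: reproduce the plan's figures.** Detectable difference = (z for two-sided alpha + z for 80% power) × √(2/n per arm), with z for 80% power = 0.842.

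- Growth, alpha 0.0125, 665 per arm: (2.498 + 0.842) × √(2/665) = 0.183 SD.
- Growth, alpha 0.0125, 522.5 per arm: (2.498 + 0.842) × √(2/522.5) = 0.207 SD. Together these reproduce 0.18 to 0.21.
- Cognitive, alpha 0.05/3, 125 per arm: (2.394 + 0.842) × √(2/125) = 0.409 SD.
- Cognitive, alpha 0.0125, 125 per arm: (2.498 + 0.842) × √(2/125) = 0.422 SD. At 0.42 SD, power is 0.823 at 0.05/3 and 0.795 at 0.0125.

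**Step 2: what the fixed level spends.** By the Bonferroni bound:

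- four tests: 4 × 0.0125 = 0.05
- three cognitive tests: 3 × 0.0125 = 0.0375
- five growth and blood pressure tests: 5 × 0.0125 = 0.0625

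The written rule is therefore exact Bonferroni only for k = 4.

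**Step 3: Holm against the written rule.** Correlated normal test statistics were simulated with at least 200,000 runs per setting. Every affected outcome has the same effect. Holm's thresholds are 0.0125, 0.0167, 0.025 and 0.05 for k = 4, and 0.0167, 0.025 and 0.05 for k = 3.

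| Family and effect | Outcomes affected | Fixed 0.0125, power per affected outcome | Holm, power per affected outcome |
|---|---|---|---|
| Growth, k = 4, 0.183 SD, N = 1330 | 1 | 0.80 | 0.80 |
| | 2 | 0.80 | 0.82 |
| | 3 | 0.80 | 0.84-0.85 |
| | 4 | 0.80 | 0.87-0.89 |
| Cognitive, k = 3, 0.42 SD, N = 250 | 1 | about 0.795 | 0.82-0.83 |
| | 2 | about 0.795 | 0.85 |
| | 3 | about 0.795 | 0.88-0.90 |

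In the cognitive rows, 0.823 - 0.795 = 0.028, or about 3 points, comes from moving from 0.0125 to 0.05/3 and needs no step-down. With one outcome affected, that is essentially the whole gain.

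With all four growth outcomes affected, power to declare all four rises from 0.41-0.62 to 0.69-0.79. Holm power per outcome falls with correlation, from 0.894 at 0 to 0.865 at 0.7. In no run did Bonferroni at 0.05/k reject an outcome that Holm did not. Holm's simulated familywise error with all nulls true and correlation 0 was 0.049 for k = 3, 4 and 5.

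**Step 4: five growth and blood pressure tests.** If the two pressures are tested separately, Holm starts at 0.05/5 = 0.01. With one outcome affected at 0.183 SD, the written 0.0125 rule has power 0.80 and Holm 0.78. The written rule's error bound is then 0.0625, however, so it no longer guarantees the 0.05 that it promises.

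**The case against.** The strongest reply is that nothing here is wrong. A fixed Bonferroni level is prespecified, simple and valid for four outcomes, and it meets the plan's own power target in the growth family. Choosing it over a sharper valid procedure for secondary outcomes is a matter of preference. That stands, and it is why this point is an improvement and not a defect.

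A reader might infer more than the documents support in four ways.

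- *Power is given away for nothing.* With k = 4, Holm leaves the chance of at least one rejection practically unchanged, and it adds nothing when only one outcome is affected. It also has a small price. Bonferroni-level simultaneous intervals (98.75% for four outcomes) match the fixed rule exactly but can include zero for an outcome that Holm declares significant. Sections 2.15.2 and 2.15.3 do not specify intervals for these outcomes, so the price is minor.
- *A real shift in several measures would be declared for only one.* With all four growth outcomes affected, exactly one is declared in 2.5-7% of trials under the fixed rule and 1.6-5% under Holm. It is rare either way. The protocol also sets no criterion that all four must be significant.
- *Holm gains most when outcomes move together.* If that means correlated measurements, the reverse is true: the gain shrinks as correlation rises. What matters is that several outcomes are truly affected. The all-four case also needs blood pressure to shift as much as growth, and the background sections report growth effects only. With three affected, the gain is 4 to 5 points.
- *Holm beats the written text in every case.* Its dominance is over 0.05/k for the right k. With five growth and blood pressure tests it can lose to the written 0.0125, as Step 4 shows.

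**Conclusion.** The point holds as an optional improvement. The fixed 0.0125 is valid for four outcomes but less powerful than Holm at the same overall two-sided 0.05. The gain per affected growth or blood pressure outcome ranges from nil with one affected to 7-9 points with all four. In the cognitive family it is about 3 to 10 points against the written rule, of which about 3 belong to the mismatch between sections 2.11.3 and 2.15.3.

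These sizes assume equal effects at the design difference, 1:1 allocation and a common correlation of 0 to 0.7. That Holm never loses to Bonferroni at 0.05/k, and that it holds the overall 0.05, needs none of these assumptions.

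**What to change.** 1. Settle the family sizes first. Reconcile the 0.0167 of section 2.11.3 with the 0.0125 of section 2.15.3, and state in sections 2.8.2 and 2.15.2 whether systolic and diastolic pressure count as one test or two.
2. In sections 2.15.2 and 2.15.3, replace the fixed nominal level with Holm's step-down within each family at an overall two-sided 0.05, and name the outcomes in each family.
3. Keep the detectable differences in sections 2.11.2 and 2.11.3 as Bonferroni-based minimum figures, restated if the reconciliation changes k or the level.
4. If simultaneous intervals are reported, keep them at the Bonferroni level and note that one may occasionally include zero for an outcome that Holm declares significant.

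The cost is about one sentence per analysis section, with no extra data and no change to the sample size. The change should be made before the single final analysis described in section 2.16.

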1.2.2 Secondary research questions

1. What is the effect of repeat courses of ACS every 14 days, vs placebo, following a single course of ACS 14-21 days prior to enrollment, on height, weight, head circumference, and blood pressure, in children at 5 years of age?
2. What is the effect of repeat courses of ACS every 14 days, vs placebo, following a single course of ACS 14-21 days prior to enrollment, on intelligence and specific cognitive (visual motor, visual spatial, and language) skills, in children at 5 years of age?

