2.15 Analysis

2.15.1 Analysis of primary outcome

Since the pregnancies used for the 5-year follow-up will be a sub-sample of the original *MACS* pregnancies, they will be compared to those not included with respect to the baseline variables: premature rupture of membranes (PROM), multiple birth (1 fetus versus 2+) and gestational age at randomisation. In addition, in the sample used for the 5-year follow-up, the treatment arms will be compared with respect to the same baseline variables. Fisher's exact tests will be used for PROM and multiple birth, and t-tests (or Mann-Whitney U test, if data are skewed) for gestational age. A two-sided Type I error of 0.05 will be used.

The primary outcome will be compared between treatment arms using a Fisher's exact test with a two-sided Type I error of 0.05. The relative risk and its corresponding 95% confidence interval will be calculated. In addition, a logistic regression analysis will be performed to compare treatment arms while controlling for PROM, multiple birth and gestational age. A multi-level model will be applied to the data using WinBUGS (version 1.4.1, see www.mrc-bsu.cam.ac.uk/bugs/welcome.shtml) to allow for random effects (intercept and slope) due to centres while also controlling for baseline variables. Using a similar analytic approach, a supportive analysis as described in the above four sentences will compare treatment arms with respect to the four domains comprising the primary outcome (death, neuromotor disability [non-ambulatory cerebral palsy], neurosensory disability [blindness, deafness, or need for visual and/or hearing aids], and abnormal cognitive score). Since pregnancy is the unit of analysis, if any child of a multiple birth has an abnormal outcome, the pregnancy will be considered to have had an abnormal outcome. If some of the data are missing, the child will only be considered to have an abnormal outcome if he or she is abnormal based on the data that are not missing.

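### The worst-sibling rule for growth, blood pressure and cognitive outcomes leaves out measured children and, when effects vary between children, does not estimate the effect in children

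*Protocol*

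**What the plan says.** Section 2.15.2 of the Protocol treats height, weight, head circumference and blood pressure as continuous: "These secondary outcomes are continuous and will be compared between treatment arms using two-sample t-tests". It adds that "Multiple linear (least-squares) regression will be used to adjust for the baseline variables". Section 2.15.1 lists these variables as premature rupture of membranes (PROM), "multiple birth (1 fetus versus 2+) and gestational age at randomisation". For siblings, Section 2.15.2 takes pregnancy as the unit of analysis and says that "the worst value for the children of multiple births will be used". Section 2.15.3 repeats that rule for intelligence and the specific cognitive skills.

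The first secondary question in Section 1.2.2 asks for the effect "on height, weight, head circumference, and blood pressure, in children at 5 years of age". The second asks about intelligence and cognitive skills, also in children. Section 2.5 includes every child of a mother randomised at a participating centre. Section 2.8.2 has growth and blood pressure assessed in all of them, and cognitive skills in children at the English-speaking centres. The protocol does not say which end of any of these scales is worst, and it plans no child-level analysis of them.

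**The concern.** For a binary outcome, counting a pregnancy as abnormal if any child is abnormal defines a clear pregnancy-level event. Carried over to centimetres, kilograms, mmHg and test scores, the same idea gives a mixture: a singleton contributes an ordinary value, while a multiple pregnancy contributes the minimum or maximum of two or more. The arm mean is then not a mean of children. The sibling who supplies the value may differ from one outcome to the next, and the other siblings' measurements go unused.

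The rule also needs a direction. Low is the natural reading for height, head circumference and test scores, and high for blood pressure. For weight at 5 years either end could be meant, so two analyses fit the same text. At stake is what the secondary estimates mean, and some precision.

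**Working it through.** **1. The plan's own figure.** Inputs: N = 1045 to 1330 pregnancies (Section 2.11.1), two-sided testing (Section 2.11.2), nominal alpha 0.0125 ("A nominal Type I error of 0.0125 will be used to maintain an overall Type I error of 0.05"), power 80%, and equal arms (assumed). Detectable difference = (2.498 + 0.842) x sqrt(4/N).

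- N = 1330: 0.183 SD
- N = 1045: 0.207 SD

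These round to the stated 0.18 and 0.21 SD. They count pregnancies, which agrees with one value per pregnancy.

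**2. Assumptions.** The protocol gives neither the share of multiple pregnancies (p) nor the correlation between siblings (rho). I take p = 10% to 30%, all twins with both assessed, and rho = 0.5 to 0.7.

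**3. Children left out of each comparison**, p/(1 + p):

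- 0.1/1.1 = 9%
- 0.2/1.2 = 17%
- 0.3/1.3 = 23%

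Per 1045 pregnancies this is about 104, 209 and 314 children.

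**4. Shift in level.** The worse of two siblings lies sqrt((1 - rho)/pi) from the child mean: 0.40 SD at rho 0.5 and 0.31 SD at rho 0.7. It lies below the mean if worst is lowest and above it if worst is highest. With the same number of siblings measured, the shift is the same in both arms.

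**5. Treatment contrast.** This was simulated with 1,000,000 twin pairs per arm, rho 0.6 and a true child-level effect of 0.20 SD that lowers the value. Affected children were drawn independently within pairs. The last two columns are 0.8 x 0.20 + 0.2 x (twin contrast), that is, 20% twins.

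| Children carrying the effect | Twins, worst = lowest | Twins, worst = highest | All, lowest | All, highest |
|---|---|---|---|---|
| all | 0.20 | 0.20 | 0.200 | 0.200 |
| 50% | 0.22 | 0.18 | 0.204 | 0.196 |
| 20% | 0.26 | 0.13 | 0.212 | 0.186 |
| 10% | 0.32 | 0.08 | 0.224 | 0.176 |

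The last row is extreme, because each affected child moves by 0.20/0.10 = 2 SD. If treatment raised the value, the lowest and highest columns would swap.

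**6. Variance, rho 0.5.** The variance of the worse of two is 1 - 0.5/pi = 0.841.

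- Worst value, unadjusted: (1 - p) + 0.841p + p(1 - p) x 0.159 = 0.998, 0.994, 0.986 at p = 10%, 20%, 30%.
- Worst value, adjusted for multiple birth: (1 - p) + 0.841p = 0.984, 0.968, 0.952.
- Every child, clustered on pregnancy: 1/[(1 - p) + 2p/1.5] = 0.968, 0.938, 0.909.

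Against the child-level analysis, the penalty is 3%, 6% and 8% unadjusted and about 2%, 3% and 5% adjusted. Over p = 10% to 30% and rho = 0.5 to 0.7, using every child would move the detectable difference from 0.207 to 0.197-0.205 SD (N = 1045), or from 0.183 to 0.175-0.182 SD (N = 1330).

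**7. Unequal numbers of siblings.** The planned covariate is the fetal count at baseline, so it does not capture how many siblings survive and attend. At 20% twins and rho 0.5, a 10-point gap between arms in complete pairs moves the contrast by 0.20 x 0.10 x 0.40 = 0.008 SD.

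**The case against.** Pregnancy as the unit is deliberate. Women are randomised, sample sizes count women, and the primary question is also phrased in terms of children yet answered per pregnancy. One value per randomised unit is a valid way to deal with clustering. Randomisation makes the level shift common to both arms, the adjusted model includes multiple birth, and the loss of precision is small. The direction of worst can be settled in a statistical analysis plan, which is not shown, and the background's concern about reduced growth hints at the low end for weight.

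Most of this stands, and it limits the size of the point. It does not remove it. The sibling rule is fixed in the protocol, not left open, and clustering can be respected without dropping siblings.

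Three stronger readings are tempting, and the documents do not support them:

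- At 20% twins and rho 0.5 the arm mean moves by 0.2 x 0.40 = 0.08 SD, and the low and high readings of weight differ by 0.16 SD in level. A reader might set these against the detectable 0.18-0.21 SD. They are levels shared by both arms, whereas 0.18-0.21 SD is a difference between arms.
- A reader might object that such means cannot be compared with growth or IQ norms. The protocol plans no such comparison for these outcomes. Its normative cut-offs apply to the two parent questionnaires in the primary outcome.
- A reader might infer that the end used for weight will be chosen after seeing the data. An analysis plan may already fix it.

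**Conclusion.** The point holds as a modest weakness in secondary analyses, not as a flaw in the validity of the tests. The rule leaves out roughly 9% to 23% of children under the assumed 10% to 30% twins. It estimates the child-level effect correctly when that effect is uniform and the arms have the same number of siblings measured. When the effect varies between children, it departs in a direction set by an end of the scale that the protocol does not name. In the most extreme case examined the departure is 0.024 SD either way from a true 0.20 SD (20% twins, rho 0.6). The variance penalty is 3-8% unadjusted and about 2-5% adjusted (rho 0.5); at rho 0.7 and 20% twins the adjusted figure is about 1.5%. All these sizes rest on assumed twin shares and sibling correlations. The case for change is that a better analysis of data already being collected costs almost nothing.

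**What to change.** In Sections 2.15.2 and 2.15.3, replace the worst-value rule with an analysis of every assessed child by linear mixed model or GEE, with pregnancy as the cluster. Adjust for the baseline variables already planned: PROM, multiple birth and gestational age. This keeps the randomised unit, matches the questions in Section 1.2.2 and needs no definition of worst. It does not remove selection through death or non-attendance.

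The cost is a change of wording, a slightly more complex model, and a unit of reporting that differs from the per-pregnancy primary outcome. No new data are needed. Further covariates (centre, sex, exact age) and a child-level GEE of the primary composite are optional and not part of this correction.

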2.15.3 Analysis of secondary outcomes: intelligence and specific cognitive skills

Since the pregnancies used for these outcomes will be an even smaller sub-sample of the original *MACS* pregnancies, they will be compared to those not included with respect to the baseline variables PROM, multiple birth and gestational age at randomisation. In addition, in the sample used for these outcomes the treatment arms will be compared with respect to the same baseline variables. Fisher's exact tests will be used for PROM and multiple birth and t-tests (or Mann-Whitney U test, if data are skewed) for gestational age. A two-sided Type I error of 0.05 will be used.

These secondary outcomes are continuous and will be compared between treatment arms using two-sample t-tests. Multiple linear (least-squares) regression will be used to adjust for the baseline variables. Transformation or ranking procedures will be used if the data are observed to be skewed. A nominal Type I error of 0.0125 will be used to maintain an overall Type I error of 0.05. Since pregnancy is the unit of analysis, the worst value for the children of multiple births will be used.

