2i) *WPPSI-III (Wechsler Preschool and Primary Intelligence Scale for Children-III edition)* is an individually administered clinical measure for assessing the intelligence of children aged 2 years 6 months to 7 years 3 months.^{52,53} The measure provides subtest and composite scores that represent intellectual functioning in verbal and performance cognitive domains as well as a composite score representing a child's general intellectual ability (IQ). Being the criterion test of preschool intelligence, the WPPSI-III has an overall reliability index of .96 and validity estimates from .78 to .89. Validity comparisons with numerous other measures have been conducted as have studies with various special groups including those with intellectual disability, developmental delay, language disorders (expressive and receptive), and with children at risk, with motor impairment and with Attention Disorder/Hyperactive Disorder (ADHD).^{54,55}

2ii) *Beery: The Developmental Test of Visual Motor Integration –5th edition (VMI)* is a sensitive, unbiased standardised instrument for measuring the development of visual and motor abilities and their integration. The VMI contains a series of 24 geometric forms that the child is required to copy until a criterion performance is reached.^{56,57} The psychometric properties include high overall reliability of .92, with strong internal consistency of .96, interscorer consistency of .94, and time sampling of .87. The VMI is considered the most valid instrument of its kind and is highly predictive in identifying children at risk for learning disabilities.

2iii) *Peabody Picture Vocabulary Test- 3rd Edition (PPVT-III)* is an individually administered, untimed, norm-referenced test that evaluates children's vocabulary knowledge development and is the hallmark tool for assessing receptive language abilities.^{58,59} The PPVT-III demonstrates high internal consistency of .95 and stability in time sampling of .91/.92. It is a valid screener with correlation coefficients for intellectual functioning (.90) and moderately predicts school achievement (.33-.80), language abilities (.42-.75), and written language (.77).⁵⁸

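### The three cognitive outcomes are planned at a nominal 0.0167 (Section 2.11.3) but tested at 0.0125 (Section 2.15.3); the mismatch is conservative but needs one consistent level

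*Protocol*

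**What the plan says.** Section 2.8.2 of the protocol lists three instruments for the English-speaking centres: the WPPSI-III, the Beery VMI and the PPVT-III. Section 2.9 names the same three.

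The power section for these outcomes, 2.11.3, states: "A nominal value of $0.05/3 = 0.0167$ was used to control type I error because there are 3 outcomes in this category". It assumes 250 women and adds: "The difference for which we have an 80% power is 0.42 standard deviations".

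The analysis section for the same outcomes, 2.15.3, plans two-sample t-tests and states: "A nominal Type I error of 0.0125 will be used to maintain an overall Type I error of 0.05".

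The value 0.0125 is derived in one place only, Section 2.11.2, for growth and blood pressure: "A nominal value of $0.05/4 = 0.0125$ was used to control type I error because there are 4 outcomes in this category". The corresponding analysis section, 2.15.2, contains the same 0.0125 sentence as Section 2.15.3. The second paragraph of Section 2.15.3 repeats Section 2.15.2 in full.

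**The concern.** One family of outcomes has two nominal levels in the same document, and the protocol gives no reason for the difference. A Bonferroni level follows from the number of tests. With three tests and an overall 0.05 the level is 0.0167, whereas 0.0125 belongs to four tests.

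Two things are at stake. A cognitive result with a p-value between 0.0125 and 0.0167 would meet the level used in planning but fail the level stated for testing. The stricter level also takes some power from the trial's smallest analysis set, about 250 pregnancies.

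**Working it through.** **Inputs**
- Number of cognitive outcomes: 3 (Sections 2.8.2, 2.9 and 2.11.3).
- Nominal level: 0.05/3 = 0.0167 (Section 2.11.3); 0.0125 (Section 2.15.3).
- Analysed pregnancies: 250 (Section 2.11.3). I assume 125 per arm, as the protocol gives no allocation ratio.
- Test: two-sample t-test (Section 2.15.3). I assume it is two-sided, as for the other outcomes.
- Stated detectable difference: 0.42 SD at 80% power (Section 2.11.3).

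**Step 1. The levels**
- 0.05/3 = 0.0167, which reproduces Section 2.11.3.
- 0.05/4 = 0.0125, which reproduces Section 2.11.2 and is the value printed in Section 2.15.3.

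**Step 2. Overall error for three tests**
- Bonferroni ceiling at 0.0125: 3 × 0.0125 = 0.0375. If the tests were independent: 1 − (1 − 0.0125)³ = 0.0370.
- Bonferroni ceiling at 0.05/3: 0.05. If independent: 1 − (1 − 0.05/3)³ = 0.0492.

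Both levels keep the overall error within 0.05. The 0.0125 level leaves 0.05 − 0.0375 = 0.0125 of the allowance unused.

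**Step 3. The stated 0.42 SD**

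Normal approximation: d = (z₁₋α/₂ + z₀.₈₀) × √(4/N), with z₀.₈₀ = 0.8416 and √(4/250) = 0.1265.
- At 0.0167: (2.394 + 0.8416) × 0.1265 = 0.409 SD.
- At 0.0125: (2.498 + 0.8416) × 0.1265 = 0.422 SD.

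The same formula at 0.0125 reproduces the range in Section 2.11.2: 0.207 SD at N = 1045 and 0.183 SD at N = 1330, against the stated 0.18 to 0.21.

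The planned test is a t-test, so I repeated the calculation with the noncentral t distribution (248 degrees of freedom). Results for N = 250:

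| Nominal level | 80%-power difference, normal | 80%-power difference, t | Power at 0.42 SD, normal | Power at 0.42 SD, t |
|---|---|---|---|---|
| 0.0167 | 0.409 SD | 0.412 SD | 82.3% | 81.8% |
| 0.0125 | 0.422 SD | 0.425 SD | 79.5% | 78.9% |

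**Step 4. What the change of level costs**

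At 0.42 SD, power drops by 82.3 − 79.5 = 2.8 points (normal) or 81.8 − 78.9 = 2.9 points (t). At 0.0125 the planned t-test falls just short of the stated 80%; at 0.0167 it exceeds it.

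**The case against.** **The error is in the safe direction.** This stands. A reader might infer from the mismatch that the overall 0.05 is breached. It is not: 0.0375 is a ceiling, and correlated tests would lie below it. What remains is that 0.0125 is not the level the protocol derives for three tests.

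**Only Section 2.15.3 states a testing rule.** Section 2.11.3 reports the level used to compute power, whereas Section 2.15.3 says what will be applied. A reader might infer that the threshold is open to choice once the data are seen. The text does not go that far, since the one stated rule for testing is the stricter one. The narrower point stands: for p-values between 0.0125 and 0.0167 that rule departs from the planned one without explanation.

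**Four cognitive constructs are named.** The protocol refers to intelligence and to visual motor, visual spatial and language skills, and four tests would justify 0.05/4. That is possible, but Section 2.11.3 counts three outcomes and only three instruments are listed. If four tests were meant, Section 2.11.3 would be the section in error, so a correction is needed on either reading.

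**Does 0.42 SD show which level was used?** A reader might infer that it was really computed at 0.0125, since the normal formula gives 0.422 there and 0.409 at 0.0167. The evidence is too thin. By the planned t-test the 0.0125 figure is 0.425, and 0.42 SD has 81.8% power at 0.0167, so the printed value is slightly cautious at its own stated level. Small changes in N also matter: 300 women at the 80% follow-up assumed in Section 2.11.1 give 240, and at 0.0167 the t-based difference is then 0.420 SD. Section 2.11.3 says 250, so this does not establish where 0.42 came from. It does show that a gap of about 0.01 SD cannot settle the matter.

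**Conclusion.** The threshold in Section 2.15.3 is wrong as written when set against the protocol's own count of three cognitive outcomes. The likeliest explanation is that the growth and blood pressure paragraph was reused without updating the level, though the document does not say so.

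The severity is minor to moderate. Type I error remains controlled. The loss is about 3 points of power at 0.42 SD, from about 82% to about 79%, on secondary outcomes in about 250 pregnancies. The primary outcome, its sample size and its 0.05 level are untouched. The power figures rest on equal arms and two-sided testing; the mismatch between the two levels rests on no assumption. The documents do not support treating 0.42 SD as a separate error.

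**What to change.** In Section 2.15.3, replace 0.0125 with 0.0167 (0.05/3), in line with the three outcomes counted in Section 2.11.3. If four cognitive tests are really intended, name the fourth and correct the count and level in Section 2.11.3 instead. Either way, one number of tests and one nominal level should appear in both sections, settled before unmasked cognitive data are seen.

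With 0.0167 in place, the detectable difference could be given as about 0.41 SD, but 0.42 SD may stay as a slightly cautious figure. The cost is one wording change in the protocol, with no effect on data collection or participants.
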